3. INTRODUCTION

This TSAP describes the statistical analyses for Part 1 of study 1368-0098.

As per ICH E9, the purpose of this document is to provide a more technical and detailed elaboration of the principal features of the analysis described in the protocol, and to include detailed procedures for executing the statistical analysis of the primary and secondary variables and other data.

This TSAP assumes familiarity with the Clinical Trial Protocol (CTP), including Protocol Amendments. In particular, the TSAP is based on the planned analysis specification as written in CTP Section 7 "Statistical Methods and Determination of Sample Size". Therefore, TSAP readers may consult the CTP for more background information on the study, e.g., on study objectives, study design and population, treatments, definition of measurements and variables, planning of sample size, randomization. In this TSAP, subject and patient will be used interchangeably.

SAS® Version 9.4 will be used for all analyses.

For Part 1 (Phase IIb):

Date: 07-08-2024, Version 1.0

Per CTP, the primary and interim analysis for Part 1 will be conducted after the last trial participant completes the Week 8 visit and Week 16 visit respectively. Separate iDBLs will be performed for primary and interim analysis and a respective team ("shadow team") independent of the main trial team will be formed to conduct the necessary analyses and ensure to maintain the blind and restrict access to the randomization codes from the main trial team for both primary and interim analysis. Details of this process will be described in a separate data logistics plan which will also specify details on data access.

Analyses of the skin and blood biomarkers will be described in a separate biomarker SAP, unless otherwise specified in this document.

Proprietary confidential information © 2024 Boehringer Ingelheim International GmbH or one or more of its affiliated companies.

4. CHANGES IN THE PLANNED ANALYSIS OF THE STUDY

All analyses stated in the CTP (latest version) will be performed as planned with the following adaptations.

The below further efficacy endpoints have been updated:

- Achievement of HiSCR50 at each scheduled assessment.
 HiSCR50 is defined as at least a 50% reduction from baseline in the total abscess and inflammatory nodule count, with no increase in the abscess or draining fistula count.
- Absolute change from baseline in Patient Global Impression of Change (PGI-C) score over time.

This endpoint will be updated to:

Patient Global Impression of Change (PGI-C) score at each scheduled assessment over time.

• Absolute change from baseline in Patient Global Impression of Severity (PGI-S) score over time.

This endpoint will be updated to:

Date: 07-08-2024, Version 1.0

Patient Global Impression of Severity (PGI-S) score at each scheduled assessment over time.

The below further efficacy endpoints, which were not specified in the CTP version 2.0, have been added:

- Achievement of HiSCR75 at each scheduled assessment.
 HiSCR75 is defined as at least a 75% reduction from baseline in the total abscess and inflammatory nodule count, with no increase in the abscess or draining fistula count.
- Achievement of HiSCR90 at each scheduled assessment.
 HiSCR90 is defined as at least a 90% reduction from baseline in the total abscess and inflammatory nodule count, with no increase in the abscess or draining fistula count.
- Achievement of mHiSCR at each scheduled assessment: mHiSCR is defined as at least a 50% reduction in total ANdT count relative to baseline. and at least 50% reduction in total dT count relative to baseline.
- Achievement of mHiSCR-AdT at each scheduled assessment: mHiSCR-AdT is defined as at least a 50% reduction in the total AdT count with no increase in inflammatory nodule count, no increase in abscess count, and no increase in dT count relative to baseline.
- Achievement of mHiSCR-AdT(2) at each scheduled assessment: mHiSCR-AdT (2) is defined as at least 50% reduction in the total ANdT count relative to baseline and at least 50% reduction in total AdT count relative to baseline.

Boehringer Ingelheim TRIAL STATISTICAL ANALYSIS PLAN 1368-0098

Date: 07-08-2024, Version 1.0

Page 10 of 64

c43421787-01

- Achievement of 2 points reduction in Physician's Global Assessment (PGA) score from baseline at each scheduled assessment (only for patients with a PGA \geq 2 at baseline).
- Achievement of at least 30% reduction from Week 1 measurement in Numerical rating scale in Patient's Global Assessment of HS pain at each scheduled assessment.
- Percent change from baseline in Numerical rating scale in Patient's Global Assessment of HS pain at each scheduled assessment
- Percent change from Week 1 in Numerical rating scale in Patient's Global Assessment of HS pain at each scheduled assessment

Proprietary confidential information © 2024 Boehringer Ingelheim International GmbH or one or more of its affiliated companies.

5. ENDPOINT(S)

5.1 PRIMARY ENDPOINT(S)

The primary endpoint of the study is defined in CTP as:

Part 1 (Phase IIb): Percent change from baseline in dT count at Week 8

5.2 SECONDARY ENDPOINT(S)

5.2.1 Key secondary endpoint(s)

Part 1 (Phase IIb): Not applicable

5.2.2 Secondary endpoint(s)

Part 1 (Phase IIb) Efficacy

Date: 07-08-2024, Version 1.0

[figure not shown]
- Percent change from baseline in dT count at Week 16.
- Absolute change from baseline in IHS4 value at Week 8.
- Absolute change from baseline in IHS4 value at Week 16.

Safety

[figure not shown]
Occurrence of treatment emergent adverse events (TEAEs)

[figure not shown]
c43421787-01

[figure not shown]
c43421787-01

[figure not shown]
c43421787-01

c43421787-01

c43421787-01

Proprietary confidential information © 2024 Boehringer Ingelheim International GmbH or one or more of its affiliated companies.

6. GENERAL ANALYSIS DEFINITIONS

6.1 TREATMENT(S)

Part 1 (Phase IIb)

Date: 07-08-2024, Version 1.0

The analysis periods are defined relative to the day of randomization (Day 1) in Table 6.1:1:

Table 6.1: 1 Flow chart of analysis periods of the study according to randomized treatment

Study analysis period	Description	Start (included)	End (included)
Screening period	Screening	Earliest of (Date of informed consent, first screening procedure)	Date/time of start of the first study dose minus 1 minute.
Loading period (from Day 1 to	On- treatment period	Date/time of start of the first study loading dose (Day 1)	Earliest of i) Date/time of start of the first maintenance dose minus1 minute; ii) Date of end of last loading dose + 112 days at 11:59 p.m. if patient early discontinued study treatment before visit; iii) last contact date on End of Study page at 11:59 p.m.
Maintenance period I (from to Week 8)		Date/time of start of the first maintenance dose for visit (if applicable)	Earliest of i) Date/time of start of the study maintenance dose for Week 8 visit minus 1minute; ii) Date of end of last maintenance dose + 112 days at 11:59 p.m. if patient early discontinued study treatment before Week 8 visit; iii) last contact date on End of Study page at 11:59 p.m.
Maintenance period II (from Week 8 to Week 16)		Date/time of start of the study maintenance dose for Week 8 visit (if applicable)	Earliest of i) Date/time of start of the study maintenance dose for Week 16 visit minus 1minute; ii) Date of end of last maintenance dose + 112 days at 11:59 p.m. if patient early discontinued study treatment before Week 16 visit; iii) last contact date on End of Study page at 11:59 p.m.
Maintenance period III (from Week 16 to		Date/time of start of the study maintenance dose for Week 16 visit (if applicable)	Earliest of i) Date/time of the first treatment in OLE trial 1368.0130 minus1 minute if subject is rolled over; ii) Date of end of last maintenance dose + 112 days at 11:59 p.m. if patient early discontinued study treatment; iii) last contact date on End of Study page at 11:59 p.m.
Off-treatment phase ¹ (if applicable)	Off- treatment period	Date of end of last study dose + 113 days at 0:00 a.m.	Latest of i) Date of EOS visit; ii) last contact date on End of Study page at 11:59 p.m.

Proprietary confidential information © 2024 Boehringer Ingelheim International GmbH or one or more of its affiliated companies.

Dates are defined individually per patient. If more than one date is associated with a specific visit, measurements associated with a specific date are assigned to a study analysis period according to the rules specified in the table. An analysis period will not extend beyond the start date of the following phase.

¹ The off-treatment period only exists for patients who early discontinued study treatment or choose not to enter the extension study 1368-0130, whose last contact date is after the date of end of last study treatment + 112 days.

The following labels for the treatment groups for all analysis is according to the randomized treatment up to Visit 14 (Week 16):

•	receive placebo);
•	"Speso Low" (
	[Week 16]);
•	"Speso Medium"
	[Week 16]);
•	
	[Week 16]):

- "Speso Total" (i.e. randomised to any of the spesolimab group);
- "Overall Total" (i.e. randomised to any treatment group regardless of placebo or Spesolimab group).

6.2 IMPORTANT PROTOCOL DEVIATIONS

Each protocol deviation must be assessed to determine whether it is an important protocol deviation(iPD). For definition of iPDs, and for the process of identification of these, refer to the BI reference document "Identify and Manage Important Protocol Deviations (iPD)" (9.6).

Handling of iPDs in analysis is included in the DV domain specifications and stored within the Trial Master File (TMF) in Electronic Document Management System (EDMS). iPDs may lead exclusion of subjects from the Per-Protocol set (PPS), which will be specified in DV domain specifications.

6.3 INTERCURRENT EVENTS

The expected intercurrent events of interest in this trial are:

Use of rescue medication

Treatment discontinuation due to AE/lack of efficacy

Treatment discontinuation due to other reasons, e.g. relocating or other logistical reasons.

Use of restricted medication

Death

Date: 07-08-2024, Version 1.0

The strategies for handling intercurrent events up to Week 16 visit are as follows:

- Treatment policy (ET): Use of "treatment policy" approach disregards the intercurrent event and uses the value of the variable regardless of the occurrence of the intercurrent event.
- Hypothetical approach (EH): Data after the intercurrent events will be censored.

Proprietary confidential information © 2024 Boehringer Ingelheim International GmbH or one or more of its affiliated companies.

- Composite strategy (EC): Use of composite approach, where data after the intercurrent events were treated as a non-responder.

If multiple intercurrent events occur to the same patient up to Week 16 visit, the intercurrent event with composite strategy will be considered.

Summary of intercurrent events and handling strategy for primary endpoint are listed in Table 6.3: 1.

Table 6.3: 1 Summary of intercurrent events and handling strategy for primary endpoint

Intercurrent Events	Primary Estimand (ET)	Supplementary Estimand (EH)
Use of rescue medication	ET	EH (Censor*)
Treatment discontinuation due to AE/lack of efficacy	ET	EH (Censor*)
Treatment discontinuation due to other reasons	ET	EH (Censor*)
Use of restricted medication	ET	EH (Censor*)
Death	ЕН	EH (Censor*)

^{*}Data after the time when intercurrent event happens will be censored.

Date: 07-08-2024, Version 1.0

Summary of intercurrent events and handling strategy for **continuous secondary and further endpoints** are listed in Table 6.3: 2.

Table 6.3: 2 Summary of intercurrent events and handling strategy for continuous secondary and further endpoints

Intercurrent events	Primary Estimand (ET)
Use of rescue medication	ET
Treatment discontinuation due to AE/lack of efficacy	ET
Treatment discontinuation due to other reasons	ET
Use of restricted medication	ET
Death	EH

1368-0098

c43421787-01

Proprietary confidential information © 2024 Boehringer Ingelheim International GmbH or one or more of its affiliated companies.

Summary of intercurrent events and handling strategy for **binary further endpoints** are listed in Table 6.3: 3.

Table 6.3: 3 Summary of intercurrent events and handling strategy for binary further endpoints

Intercurrent events	Primary Estimand (EC-ET)
Use of rescue medication	EC
Treatment discontinuation due to AE/lack of efficacy	ET
Treatment discontinuation due to other reasons	ET
Use of restricted medication	EC
Death	EC

Primary Imputation Approach for binary endpoints – No Response Imputation [NRI]:

- If there are data at visits both before and after the visit with a missing outcome, then impute as success only if both neighbouring visits also represent a success (independent of whether the preceding and following observations were selected for analysis based on time windows described in Section 6.7 and no rescue treatment has been given during this period).
- Otherwise, impute as a failure.

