resulting in paraesthesia, reduced sensibility, and/or pain for an indefinite period.	mark) at the puncture site. Furthermore, there is a small risk of lightheadedness and/or fainting. In rare cases, the puncture site can also become infected, or nerves may be damaged, inducing long-lasting abnormal sensations (paresthesia), impaired sensation of touch and persistent pain.	These risks will be addressed by careful safety monitoring and risk mitigation measures such as  (a) pressure on the puncture site for approximately 5 minutes after the needle extraction, is recommended.  (b) close clinical monitoring for AEs.  (c) selection of experienced sites and site staff.  (d) safety recommendations provided in laboratory	
Skin biopsy	Can cause local bruising, inflammation, nerve damage and pain.	manual.  These risks will be addressed by careful safety monitoring and risk mitigation measures such as  (a) close clinical monitoring for AEs.  (b) selection of experienced sites and site-staff.  (c) staff training.	

Page 37 of 177

Proprietary confidential information © 2023 Boehringer Ingelheim International GmbH or one or more of its affiliated companies

Table 1.4.2: 1 Overview of trial-related and potential risks (cont.)

Other risks		
Administration of placebo	If the trial participant is randomised to receive a placebo, the participant's condition could get worse during the trial.	The placebo control is required to control for investigator bias and/or beneficial effects of being in a clinical trial. The rationale for switching placebo trial participants to active treatment at Visit 14 is to give these trial participants the opportunity to receive active investigational medicinal product (IMP) treatment from that visit.
		The use of rescue medication is foreseen in this trial for participants experiencing a worsening of their HS condition; see Section 4.2.3 .

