From Visit 14 , there is an option of increasing the dose to the maximum subcutaneous dose of applied to low dose treatment group participants only, via IRT in a blinded manner) if they have compared to baseline and the investigator agrees with the dose increase.
For trial participants initially randomised to placebo group, from Visit 10 to Visit 13 (both inclusive), the participants will be administered a matching placebo Visit 14 to Visit 31 (both inclusive), the participants will be dose of spesolimab
From Visit 23 on, trial participants will continue to receive the assigned dosing regimen, at least until the results of are available. Upon availability of the Phase IIb (Part 1) primary analysis efficacy and safety results, the dosing regimen may be adapted from Visit 23. For more detailed drug assignment and administration of doses for each trial participant, please see Section 4.1.5.
Follow-up phase and end of study  Trial participants completing EoT visit of the study may roll over to an if they agree and meet the eligibility criteria. These trial participants are not required to complete a safety follow-up period, and their EoT visit will be considered also their end of study (EoS) visit, which is the
Trial participants, who permanently discontinue trial drug earlier than Visit 31 do not qualify to enter the LTE trial for any other reason, will be invited to do the EoT visit instead of the next planned visit and will then enter a safety follow-up period

BI Trial No.: 1368-0098

c40061625-02 Clinical Trial Protocol Page 48 of 177

Proprietary confidential information © 2023 Boehringer Ingelheim International GmbH or one or more of its affiliated companies

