#### Part 2 (Phase III)

### Efficacy endpoints

In the primary analysis of primary and continuous key secondary endpoints, missing data will not be imputed except for death (unexpected), where a poor outcome will be assigned. The mixed effect model will handle missing data based on a likelihood method under the 'missing at random assumption'.

Sensitivity analyses for handling missing primary and continuous key secondary endpoints data will be specified in the TSAP.

In the primary analysis of binary key secondary endpoints, a No Response Imputation (NRI) approach will be applied to the missing visits up to that is, imputing as a failure to achieve a response in the visits with missing endpoint score, however:

- If there are available data at the visits both before and after the visit with a missing outcome, then impute as a success only if both the preceding and the following measurement indicate success.
- Otherwise, impute as a failure to achieve a response (i.e. no response imputation)

NRI is a conservative imputation scheme because it assumes that missing data due to any reason is related to treatment failure.

Sensitivity analyses for handling missing binary key secondary endpoints data will be specified in the TSAP.

Full details on the handling of missing data will be specified in the TSAP prior to unblinding.

Page 115 of 177

Proprietary confidential information © 2023 Boehringer Ingelheim International GmbH or one or more of its affiliated companies

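### A missing Week 16 binary outcome can be imputed as a success partly from a visit made after the placebo arm has switched to spesolimab

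*SAP*

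**What the plan says.** SAP 6.3 gives the primary imputation for binary endpoints, after Table 6.3: 3. It has three elements.

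- Trigger: "If there are data at visits both before and after the visit with a missing outcome". No limit is set on how late the following visit may be.
- Condition: "then impute as success only if both neighbouring visits also represent a success". Anything else is a failure.
- Source values: neighbours are used "independent of whether the preceding and following observations were selected for analysis based on time windows described in Section 6.7", provided that "no rescue treatment has been given during this period".

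The intercurrent events listed in SAP 6.3 do not include the planned change of treatment at Week 16. The Week 16 limit in that section governs the intercurrent-event strategies, not which visits may feed the imputation.

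Protocol Table 1.4.2: 1 explains the reason for "switching placebo trial participants to active treatment at Visit 14", and protocol 3.1 has the placebo group on active drug over "Visit 14 to Visit 31 (both inclusive), the participants will be dose of spesolimab". SAP 6.1 equates Visit 14 with Week 16 and labels patients by randomised arm. SAP 6.4 analyses efficacy by planned arm. Protocol 3.1 also gives the low-dose arm, and no other, an option of a higher dose from Visit 14.

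SAP section 3 states that "Separate iDBLs will be performed for primary and interim analysis", the interim one being at Week 16. SAP section 7 adds a final analysis at study end.

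For Part 2, protocol 7.3 has a parallel rule for binary key secondary endpoints: "If there are available data at the visits both before and after the visit with a missing outcome". It limits the visits that are imputed, with the time point blacked out, but not the visits used as sources.

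**The concern.** Week 16 is the last placebo-controlled time point. The value of a placebo patient there should rest on what happened on placebo. As written, the rule can settle a missing Week 16 outcome with a count taken on spesolimab and report it under placebo. This crosses a boundary that the SAP draws elsewhere: Table 6.1: 1 closes the second maintenance period one minute before the Week 16 dose, and SAP 6.4 creates a separate set for efficacy data after Week 16.

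The low-dose arm is open in the same way through its option from Visit 14. That route is narrower, because the synopsis ties the option to inadequate clinical response.

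The second issue is reproducibility. At the Week 16 lock, an early-enrolled patient may already have a later visit while an otherwise identical late-enrolled patient does not. The first can be a success and the second must be a failure. The second patient's Week 16 value can then change at the final analysis.

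**Working it through.** The documents attach no figure to this rule, so there is nothing to reproduce. The check traces the rule and then bounds its effect.

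**Trace for a placebo patient with Week 16 missing**

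| Preceding visit (placebo) | Following visit (after switch) | Imputed Week 16 |
|---|---|---|
| success | success | success |
| failure | success | failure |
| success | none yet | failure |
| success | success, rescue in between | failure |

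The first row is the problem. The third row can turn into the first between the Week 16 lock and the final analysis. If sources after the switch are barred, the first row becomes a failure and the others do not change.

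**Can the following count really come after the switch?** Yes, though not always. Protocol 6.1 recommends lesion counts before dosing, so a patient who misses Visit 14 entirely may have the next count before any active dose. Two routes lead past the switch: dosing at Visit 14 without a valid count, or an intervening dose before the next count. The second is realistic. Visit 15 may be a home visit, and the home-nurse list in protocol 6.2 includes study drug but no lesion count.

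**Inputs for the size**

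- p = placebo success rate, taken as equal at the preceding visit and at Week 16: 26-28%. This is the placebo HiSCR50 range that protocol 1.1 gives for the approved biologic, used only as an illustration.
- m = share of placebo patients with Week 16 missing and a later count available: assumed 5-20%.
- r = probability that the following visit is a success, given success at the preceding one: assumed, at most 1.

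**Formulas**

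- Rule as written: p(1 - m) + m·p·r
- Later visit barred: p(1 - m)
- Difference, counting every bridged success: m·p·r, at most m·p

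| m | Later visit barred | Rule as written, r = 1 | Largest gain (m·p) |
|---|---|---|---|
| 5% | 24.7-26.6% | 26-28% | 1.3-1.4 points |
| 10% | 23.4-25.2% | 26-28% | 2.6-2.8 points |
| 20% | 20.8-22.4% | 26-28% | 5.2-5.6 points |

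With m = 5-10% and r = 60-80%, the gain runs from 0.05 × 0.26 × 0.60 = 0.78 points to 0.10 × 0.28 × 0.80 = 2.24 points.

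**Part due to active drug.** Some of these patients would have stayed responders on placebo. The excess is m·p·(r on active − r on placebo). If the two continuation rates differ by 10-30 points (assumption), it runs from 0.05 × 0.26 × 0.10 = 0.13 points to 0.10 × 0.28 × 0.30 = 0.84 points.

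**The case against.** The strongest reply is that the rule already contains a safeguard and that little hangs on it. Much of that stands.

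- A reader might infer that a response on spesolimab alone makes a placebo responder. It does not: the preceding placebo visit must also be a success.
- A reader might take the 0.78-2.24 points as contamination by active drug. They count every bridged placebo success; the drug-related excess is smaller.
- The missing rate that matters is narrower than all missing Week 16 counts. Patients who stop treatment before Visit 14 are asked to continue efficacy visits only up to Visit 14 (protocol 3.3.4); without a later count they are failures already. The extended windows of SAP 6.7 may also accept a late Visit 14 as Week 16. For stricter endpoints such as HiSCR75 and HiSCR90, p cannot exceed the HiSCR50 rate.
- In Part 1 the rule serves binary further endpoints, which protocol 7.2.5 calls exploratory. The primary and secondary efficacy endpoints are continuous and analysed by MMRM.
- A reader might infer that dependence on enrolment date biases the comparison. With concurrent randomisation, no imbalance between arms is expected. What remains is that one patient's value can differ between snapshots.
- A reader might carry the point over to Part 2 as established. The switch time in protocol 3.1 and the imputation limit in protocol 7.3 are not legible, and the key secondary endpoints may still be amended.

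It can also be said that the SAP keeps its analysis periods separate at Week 16, and that the window tables and further-endpoint sections are not visible. A limit there cannot be excluded. However, the rule in SAP 6.3 expressly sets window selection aside for its source visits and does not refer to the analysis periods, so nothing legible closes the gap.

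**Conclusion.** The concern holds in limited form. Under the legible text of SAP 6.3, a placebo patient who was a success at the preceding visit, has no Week 16 outcome and is a success at a count taken after the first active dose is scored a Week 16 placebo responder. That value can also differ between the Week 16 lock and the final analysis.

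The effect is small. The ceiling for all bridged placebo successes is 2.6-2.8 points at 10% missing, and the drug-related part is 0.13-0.84 points on the assumptions shown. The documents give neither the missing rate nor the continuation rates, and p is borrowed from background data. In the placebo arm the bias runs against spesolimab. The low-dose route would act in that arm's favour. The rule also fills outcomes in the active arms, so the net effect on the differences is not known.

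In Part 1 the documents do not support reading this as a threat to the primary or secondary efficacy results. For Part 2 the point is conditional: it applies if the visit of a binary key secondary endpoint is the last one before placebo patients switch.

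**What to change.** Add one sentence to SAP 6.3: for outcomes up to and including Week 16, only observations made before the patient's first dose given at or after Visit 14 may serve as the following visit; if there is none, impute failure; apply this identically at the Week 16 lock and at the final analysis. A late count taken before dosing still qualifies. Using the same rule in all arms also covers the low-dose option.

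Carry the same limit into protocol 7.3 with the Part 2 amendment if the binary key secondary endpoint visit there is the last before the placebo switch.

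The cost is one sentence in each document and a few more imputed failures in all arms.
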